### **Probably Related** – The adverse event

- Follows a reasonable temporal sequence from drug administration
- Abates upon discontinuation of the drug
- Cannot be reasonably explained by the known characteristics of the patient's clinical state

#### **Possibly Related** – The adverse event

- Follows a reasonable temporal sequence from drug administration
- Could have been produced by the patient's clinical state or by other modes of therapy administered to the patient

#### **Unlikely Related** - The adverse event

- Does not follow a reasonable sequence from drug administration
- Is readily explained by the patient's clinical state or by other modes of therapy administered to the patient

#### **Unrelated** – The adverse event

- Does not follow a reasonable sequence from drug administration
- Is readily explained by and considered by the Principal Investigator to be an expected complication of the patient's primary malignancy, clinical state, concurrent medical conditions, or by other modes of therapy administered to the patient

A **protocol-related adverse event** is an AE occurring during a clinical study that is not related to the investigational treatment, but is considered by the Investigator and/or the Sponsor's Medical Monitor (or designee) to be related to the research conditions, i.e., related to the fact that a patient is participating in the study. For example, a protocol-related AE may be an untoward event related to a medical procedure required by the protocol (e.g. bleeding from a protocol-required biopsy).

# 20.3 Serious Adverse Event (SAE)

All AEs will be evaluated for seriousness. A **serious adverse event** (SAE) is an AE that meets at least one of the following criteria:

- Results in death (NOTE: death is an outcome, not an event)
- Is life-threatening
- Requires inpatient hospitalization or prolongation of an existing hospitalization
- Results in a persistent or significant disability or incapacity
- Results in a congenital anomaly or birth defect
- Additionally, important medical events that may not result in death, be life-threatening, or require hospitalization may be considered SAEs when, based on appropriate medical judgment, they may jeopardize the patient and may require medical or surgical intervention to prevent one of the outcomes listed in this definition. Examples of such events include allergic bronchospasm requiring intensive treatment in an emergency room or at home, blood dyscrasias or convulsions that do not result in hospitalization, or development of drug dependency or drug abuse.

**Life-threatening**, in the context of an SAE, refers to immediate risk of death as the event occurred per the reporter. A life-threatening experience does not include an experience, had it occurred in a more severe form, which might have caused death, but as it actually occurred,

did not create an immediate risk of death. For example, hepatitis that resolved without evidence of hepatic failure would not be considered life-threatening, even though hepatitis of a more severe nature can be fatal. Similarly, an allergic reaction resulting in angioedema of the face would not be life-threatening, even though angioedema of the larynx, allergic bronchospasm, or anaphylaxis can be fatal.

**Hospitalization** is official admission to a hospital. Hospitalization or prolongation of a hospitalization constitutes criteria for an AE to be serious; however, it is not in itself considered a serious adverse event (SAE). In the absence of an AE, a hospitalization or prolongation of a hospitalization should not be reported as an SAE. This is the case in the following situations:

- The hospitalization or prolongation of hospitalization is needed for a procedure required by the protocol. Day or night survey visits for biopsy or surgery required by the protocol are not considered serious.
- The hospitalization or prolongation of hospitalization is part of a routine procedure followed by the center (e.g., stent removal after surgery). This should be recorded in the study file.
- Emergency room visit less than 24hrs or other department visits that do not result in hospitalization (if the case is not considered as important medical or life-threatening event) is not included as SAE.
- Hospitalization for survey visits or annual physicals falls into the same category.

In addition, hospitalizations planned before the start of the study, for a preexisting condition that has not worsened, do not constitute an SAE.

**Disability** is defined as a substantial disruption in a person's ability to conduct normal life functions.

If there is any doubt about whether the information constitutes an SAE, the information is treated as an SAE.

# 20.4 Other Reportable Information

Certain information, although not considered an SAE, must be recorded, reported, and followed up as indicated for an SAE. This includes:

- A case involving a pregnancy exposure to the investigational therapy. Please refer to Section 20.4.1 for further details and requirements. Pregnancies occurring up to 6 months after completion of the study treatment must also be reported to the Investigator.
- Overdose (e.g., a dose higher than that indicated in the protocol) with or without an AE. If an adverse event(s) is associated with or results from an overdose of one or more of the investigational agents, the event must be reported as an SAE, even if no other criteria for SAE are met. Any overdoses of pembrolizumab must be reported to the Sponsor and to Merck Global Safety (Attn: Worldwide Product Safety; [contact]) within 24 hours.
- Abuse (e.g., use for nonclinical reasons) with or without an AE
- Inadvertent or accidental exposure with or without an AE

# 20.4.1 Contraception and Pregnancy

GX-188E and pembrolizumab may have adverse effects on a fetus in utero. Furthermore, it is not known if pembrolizumab has transient adverse effects on the composition of sperm.

Participants should be informed that taking the study medication may involve unknown risks to the fetus (unborn baby) if pregnancy were to occur during the study. In order to participate in the study, participants of childbearing potential must adhere to the contraception requirement (from the day of study medication initiation, or 14 days prior to the initiation of study medication for oral contraception) throughout the study period up to 120 days after the last dose of study medication. If there is any question that a participant of childbearing potential will not reliably comply with the requirements for contraception, that participant should not be entered into the study.

# 20.4.1.1 Acceptable Methods of Contraception

Highly effective methods are defined as those that result in a low failure rate (ie, less than 1% per year) when used consistently and correctly. Below is a list of highly effective methods of contraception:

- Intrauterine device (IUD)
- Hormonal (birth control pill, injections, implants, patch)
- Tubal ligation
- Partner's vasectomy

Additional effective methods (barriers) are noted below:

- Male condom with spermicidal agent
- Diaphragm or cervical cap with spermicidal agent

Abstinence is acceptable if this is the usual lifestyle and preferred contraception for the subject. The reliability of sexual abstinence should be evaluated in relation to the duration of the clinical trial and the preferred and usual lifestyle of the subject. Periodic abstinence (eg., calendar, or post-ovulation symptothermal methods) and withdrawal are NOT acceptable methods alone and must be supplemented with one of the methods considered highly effective, listed above

# 20.4.2 **Pregnancy**

.If a participant inadvertently becomes pregnant while on study, the participant will be immediately discontinued from study treatment. The site will contact the participant at least monthly and document the participant's status until the pregnancy has been completed or terminated. The outcome of the pregnancy will be reported to the Sponsor without delay and within 24 hours if the outcome is a serious adverse experience (e.g., death, abortion, congenital anomaly, or other disabling or life-threatening complication to the mother or newborn). The study investigator will make every effort to obtain permission to follow the outcome of the pregnancy and report the condition of the fetus or newborn to the Sponsor.

# 20.4.3 Use in Nursing Women

It is unknown whether pembrolizumab is excreted in human milk. Since many drugs are excreted in human milk, and because of the potential for serious adverse reactions in the nursing infant, participants who are breastfeeding are not eligible for enrollment.

# 20.5 Unexpected AE and SAE

An AE is considered *unexpected* if it is not listed in the investigator brochure or package insert for GX-188E or pembrolizumab, is not listed at the specificity or severity that has been observed, or, is not consistent with the risk information described.

"Unexpected," as used in this definition, also refers to adverse events that are mentioned in the investigator brochure or package inserts as occurring with a class of drugs or as anticipated from the pharmacological properties of the drug, but are not specifically mentioned as occurring with the particular drug under investigation.

Adverse events that would be anticipated to occur as part of the disease process are not considered *unexpected* if the event is clearly due to disease progression.

# 20.6 Reporting and Follow-Up Requirements for Adverse Events, Serious Adverse Events and Other Reportable Safety Events

# 20.6.1 Time Period and Frequency for Collecting AE, SAE and Other Reportable Safety Event Information

- All AE's or ECI's = from the time of treatment through **30 days** following cessation of study treatment
- All SAE's =90 days following cessation of study treatment, or 30 days following cessation of study treatment if the participant initiates new anticancer therapy, whichever is earlier
- All pregnancies and exposure during breastfeeding, from the time of treatment through
   120 days following cessation of study treatment, or 30 days following cessation of study treatment if the participant initiates new anticancer therapy
- Additionally, any SAE brought to the attention of an investigator at any time outside
  of the time period specified above must be reported immediately to the Sponsor if the
  event is considered to be drug-related.

The Investigator must follow-up on all treatment-related AEs, SAEs, and other reportable events until the events have subsided, returned to baseline, the patient has initiated any other anti-cancer treatment, or in case of permanent impairment, until the condition stabilizes.

All AEs and SAEs must be recorded on source documents and collected in EDC.

Although AEs should be based on the signs or symptoms detected during the physical examination and on clinical evaluation of the patient, a specific diagnosis should be reported as the AE whenever feasible. In addition to the information obtained from those sources, the patient should be asked the following nonspecific question: "How have you been feeling since your last visit?" Signs and symptoms should be recorded using standard medical terminology.

Any unanticipated risks to the patients must be reported promptly to the IRB/IEC.

# 20.7 Serious Adverse Event (SAE)-Specific and Expedited Reporting

All SAEs, other reportable information, and SAE follow-up information must be reported within 24 hr of learning of the event by completing the Adverse Event eCRF in the Medidata database. Genexine, Inc (or designee) will process and evaluate all SAEs as soon as the reports are received. For each SAE received, Genexine, Inc. (or designee) will make a determination as to whether the criteria for expedited reporting have been met.

Genexine, Inc. (or designee) is responsible for reporting relevant SAEs to the relevant regulatory authorities and participating Investigators, in accordance with FDA regulations 21 CFR 312.32, ICH Guidelines, European Clinical Trials Directive (Directive 2001/20/EC), and/or local regulatory requirements. To meet this requirement, Genexine, Inc. (or designee) may request additional information from the sites, including but not limited to, hospitalization records. Any requests for such information should be addressed in a timely manner.

Reporting of SAEs by the Investigator to the Institutional Review Board (IRB) or Ethics Committee (EC) will be done in accordance with the standard operation procedures and policies of the IRB/EC. Adequate documentation must be maintained showing that the IRB/EC was properly notified.

Adverse Events that are considered related to the investigational treatment, unexpected and serious will be reported as an IND Safety Report to the FDA in accordance with the standards set in the Code of Federal Regulations [21 CFR 312.32 (c)(1), 21 CFR 312.32(c)(2), 21 CFR 312.32(d)(2)].

#### 20.8 Events of Clinical Interest (ECI)

Selected non-serious and serious AEs are also known as Events of Clinical Interest (ECI) and must be recorded as such on the Adverse Event electronic case report forms and reported within 24 hours to the Sponsor.

#### ECIs for this trial include:

- An overdose of investigational product that is not associated with clinical symptoms or abnormal laboratory results.
- an elevated AST or ALT lab value that is greater than or equal to 3X the upper limit of normal and an elevated total bilirubin lab value that is greater than or equal to 2X the upper limit of normal and, at the same time, an alkaline phosphatase lab value that is less than 2X the upper limit of normal, as determined by way of protocol-specified laboratory testing or unscheduled laboratory testing\*.

\*Note: These criteria are based upon available regulatory guidance documents. The purpose of the criteria is to specify a threshold of abnormal hepatic tests that may require an additional evaluation for an underlying etiology. The trial site guidance for assessment and follow up of these criteria can be made available. It may also be appropriate to conduct additional evaluation for an underlying etiology in the setting of abnormalities of liver blood tests including AST, ALT, bilirubin, and alkaline phosphatase that do not meet the criteria noted above. In these cases, the decision to proceed with additional evaluation will be made through consultation between the study investigators and the Sponsor Clinical Director. However, abnormalities of liver blood tests that do not meet the criteria noted above are not ECIs for this trial.

ECIs that occur in any patient from the date of first dose through 30 days following cessation of treatment, or the initiation of a new anticancer therapy, whichever is earlier, whether or not related to the investigational product, must be reported within 24 hours to the Sponsor.

#### 20.9 Treatment of Pembrolizumab Overdose

For this study, an overdose of pembrolizumab will be defined as any dose of 1000 mg or  $\geq$ 5 times the indicated dose.

No specific information is available on the treatment of overdose of pembrolizumab. In the event of overdose, the participant should be observed closely for signs of toxicity.

Appropriate supportive treatment should be provided if clinically indicated.

#### 21.0 **Dose-Limiting Toxicities (DLTs)**

All toxicities will be graded using NCI-CTCAE Version 4.0 or the most recent version based on the investigator assessment.

The DLT window of observation will be during Cycle 1 of pembrolizumab (ie., the first 3 weeks of treatment prior to Week 4 Day 1 visit). A DLT is defined as any AE that is not clearly due to progression of the patient's primary malignancy, occurs within the DLT window of observation period, and that meets at least one of the criteria below:

### Non-Hematologic Dose Limiting Toxicities:

- Any CTCAE (v4.0 or the most recent version) Adverse Event of ≥ Grade 3 treatment-related non-hematological toxicity *except the following*:
  - o nausea, vomiting, or diarrhea lasting  $\leq 72 \text{ hr}$
  - o Grade 3 fatigue lasting  $\leq 7$  days
  - o hypersensitivity reactions lasting  $\leq$  72 hrs
  - $\circ$  Grade 3 hyperglycemia lasting  $\leq$  72 hr with standard anti-diabetic therapy
  - o Grade 3 increases in liver transaminases in patients with liver metastases. (Note: Grade 4 increases in LFTs in any patient will be considered a DLT)
  - o clinical laboratory abnormalities that are reversible to ≤ Grade 1 or baseline status within 72 hr with outpatient care and/or monitoring, or that are considered *not* clinically significant by the Principal Investigator

### Hematologic Dose Limiting Toxicities:

- Grade 4 neutropenia (ANC  $< 0.5 \times 10^9/L$ )
- Grade 3 febrile neutropenia (ANC <  $1.0 \times 10^9$ /L with temperature  $\ge 38.3$ °C)
- Grade 4 thrombocytopenia (platelet count  $< 25.0 \times 10^9/L$ ) lasting > 4 days or that requires platelet transfusion
- Grade  $\geq$  3 thrombocytopenia (platelet count < 50.0 x 10^9/L) associated with Grade  $\geq$  3 bleeding

• Any hematologic toxicity resulting in death (i.e. Grade 5)

In addition, any other AE that is felt to be treatment-limiting in the medical opinions of the Principal Investigator and the Sponsor's Medical Monitor may be considered a DLT. These include, but are not limited to the following:

- Any toxicity leading to more than one missed dose of either GX-188E or pembrolizumab during the DLT-evaluation period
- Any toxicity leading to > 2 weeks delay in initiation of the  $2^{nd}$  cycle of pembrolizumab

#### 22.0 Evaluation and Reporting of Efficacy Data

### 22.1 Tumor Imaging and Assessment of Disease

For the abdomen and pelvis, contrast-enhanced magnetic resonance imaging (MRI) may be used when CT with iodinated contrast is contraindicated, or when mandated by local practice. MRI is the strongly preferred modality for imaging the brain. The same imaging technique regarding modality, ideally the same scanner, and the use of contrast should be used in a participant throughout the study to optimize the reproducibility of the assessment of existing and new tumor burden and improve the accuracy of the assessment of response or progression based on imaging.

#### 22.1.1 **Initial Tumor Imaging**

Initial tumor imaging at Screening must be performed within 28 days prior to the date of treatment initiation. The site study team must review screening images to confirm the participant has measurable disease per RECIST 1.1.

The screening images must be submitted to the central imaging vendor for confirmation of measurable disease per RECIST 1.1 for eligibility prior to treatment initiation.

# 22.1.2 **Tumor Imaging During the Study**

The first on-study imaging assessment should be performed approximately 9 weeks ( $\pm 3$  days]) from the date of treatment initation. Subsequent tumor imaging should be performed every 9 weeks ( $\pm 3$  days at Week 19,  $\pm 7$  days for subsequent timepoints) or more frequently if clinically indicated. Imaging timing should follow calendar days and should not be adjusted for delays

in cycle starts. Imaging should continue to be performed until disease progression is identified by the investigator (unless the investigator elects to continue treatment and follow iRECIST), the start of new anticancer treatment, withdrawal of consent, or death, whichever occurs first. All supplemental imaging must be submitted to the central imaging vendor.

Objective response and stable disease should be confirmed by a repeat imaging assessment. Tumor imaging to confirm SD, PR or CR should be performed at least 4 weeks after the first indication of a response is observed. Participants will then return to regular scheduled imaging, starting with the next scheduled imaging time point. Participants who receive additional imaging for confirmation do not need to undergo the next scheduled tumor imaging if it is less than 4 weeks later; tumor imaging may resume at the subsequent scheduled imaging time point. Note: Response does not typically need to be verified in real time by the central imaging vendor.

Per iRECIST (Appendix 6 and Section 22.3), disease progression should be confirmed by the site 4 to 8 weeks after site-assessed first radiologic evidence of PD in clinically stable participants. Participants, who have unconfirmed disease progression may continue on treatment at the discretion of the investigator until progression is confirmed by the site, provided they have met the conditions detailed in Section 22.3. Participants who receive confirmatory imaging do not need to undergo the next scheduled tumor imaging if it is less than 4 weeks later; tumor imaging may resume at the subsequent scheduled imaging time point, if clinically stable. Participants, who have confirmed disease progression by iRECIST, as assessed by the site, will discontinue study treatment. Exceptions are detailed in Section 22.3.

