#### 22.1.3 End of Treatment and Follow-Up Tumor Imaging

For participants who discontinue study treatment, tumor imaging should be performed at the time of treatment discontinuation (±4 week window). If previous imaging was obtained within 4 weeks prior to the date of discontinuation, then imaging at treatment discontinuation is not mandatory. For participants who discontinue study treatment due to documented disease progression, this is the final required tumor imaging if the investigator elects not to implement iRECIST.

For participants who discontinue study treatment without documented disease progression, every effort should be made to continue monitoring disease status by tumor imaging using the same imaging schedule used while on treatment (every 9 weeks) until the start of a new anticancer treatment, disease progression, pregnancy, death, withdrawal of consent, or the end of the study, whichever occurs first.

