#### 22.3 iRECIST Assessment of Disease

iRECIST is based on RECIST 1.1, but adapted to account for the unique tumor response seen with immunotherapeutic drugs. iRECIST will be used by the Investigator to assess tumor response and progression, and make treatment decisions. When clinically stable, participants should not be discontinued until progression is confirmed by the Investigator, working with local radiology, according to the rules outlined in Appendix 6. This allowance to continue treatment despite initial radiologic PD takes into account the observation that some participants can have a transient tumor flare in the first few months after the start of immunotherapy, and then experience subsequent disease response. This data will be captured in the clinical database.

Clinical stability is defined as the following:

- Absence of symptoms and signs indicating clinically significant progression of disease
- No decline in ECOG performance status
- No requirements for intensified management, including increased analgesia, radiation, or other palliative care

Any participant deemed **clinically unstable** should be discontinued from study treatment at site-assessed first radiologic evidence of PD, and is not required to have repeat tumor imaging for confirmation of PD by iRECIST.

If the Investigator decides to continue treatment, the participant may continue to receive study treatment and the tumor assessment should be repeated 4 to 8 weeks later to confirm PD by iRECIST, per Investigator assessment. Images should continue to be sent in to the central imaging vendor for potential retrospective BICR.

If repeat imaging does not confirm PD per iRECIST, as assessed by the Investigator, and the participant continues to be clinically stable, study treatment may continue and follow the regular imaging schedule. If PD is confirmed, participants will be discontinued from study treatment.

If a participant has confirmed radiographic progression (iCPD) as defined in Appendix 6, study treatment should be discontinued; however, if the participant is achieving a clinically meaningful benefit, an exception to continue study treatment may be considered following consultation with the Sponsor. In this case, if study treatment is continued, tumor imaging should continue to be performed following the intervals as outlined in the Schedule of Events (Appendix 1) and submitted to the central imaging vendor.

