# GX-188E/Pembrolizumab [Protocol Number: GX-188E-005] Amended (V4.0)\_29Aug2022

[figure not shown]
17. Radiographic evaluations of tumor burden by RECIST v1.1 will be performed by a blinded independent central reviewer at Screening, approximately every 9 weeks during the treatment period, or more frequently as clinically indicated, and at End of Study if the reason for discontinuation is other than for confirmed radiologic disease progression. Scans obtained within 28 days prior to Week 1 Day 1 will be accepted for Screening and do not need to be repeated unless a clinically significant difference is suspected. Confirmatory scans are required approximately 4 weeks after any scan that indicates either an objective response, stable disease or disease progression,

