#### 15. EFFICACY OUTCOMES

Tumor response to treatment will be evaluated using both RECIST v1.1 and iRECIST. For each patient with objectively measurable disease and who meet the criteria for inclusion in the Efficacy Evaluable population, response to therapy will be calculated. The analysis of ORR24, BORR and DCR per RECIST v1.1 will also be performed in safety population as sensitivity analysis.

RECIST 1.1 will be used by BICR as the primary measure for assessment of tumor response, date of disease progression, and as a basis for all protocol guidelines related to disease status (e.g., discontinuation of study treatment). All efficacy endpoints will be evaluated and categorized using RECIST 1.1. Confirmatory scans are required for all determinations of objective response [Partial response (PR) or Complete response (CR)], Stable disease (SD) and disease progression (PD). Confirmatory scans must be performed at least 4 weeks later.

Investigator assessment of tumor response based upon RECIST v1.1 will be analyzed in the same way as the corresponding BICR-assessed endpoints (except Kaplan-Meier curves which will only be presented for BICR assessment). Concordance between BICR and Investigator assessments will be summarized at a patient level for BOR.

iRECIST is based on RECIST 1.1, but adapted to account for the unique tumor response seen with immunotherapeutic drugs. iRECIST will be used by the investigator to assess tumor response and progression and make treatment decisions. When clinically stable, participants should not be discontinued until progression is confirmed by the Investigator, working with local radiology, according to the rules outlined in Appendix 6 of protocol. This allowance to continue treatment despite initial radiologic PD takes into account the observation that some participants can have a transient tumor flare in the first few months after the start of immunotherapy, and then experience subsequent disease response. This data will be captured in the clinical database.

Efficacy endpoints are as follows.

- Objective Response Rate within 24 weeks (ORR24)
- Best Overall Response Rate (BORR)
- Progression-Free Survival including 6-month PFS rate and median PFS time
- Overall Survival including 6-month OS rate and median OS time
- Disease Control Rate
- Duration of Response
- Time to Best Response

Document: \(\)\ieedc-vnac01\\Biosdata\\Genexine\\GX-188E\\GYA02599\\Biostatistics\\Documentation\\SAP\)

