BICR-assessed PFS and investigator-assessed PFS by RECIST v1.1 will be displayed for Part A, Part B and Part C.

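### BICR PFS and DOR: investigator progression that BICR does not read as progression is usually censored, probably informatively, and the SAP neither counts these patients nor tests the effect

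*Protocol*

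**What the plan says.** **End of imaging.** Protocol 22.1.2: "Imaging should continue to be performed until disease progression is identified by the investigator", unless the investigator continues treatment under iRECIST. Protocol 22.1.3 says of patients stopped for documented progression that "this is the final required tumor imaging if the investigator elects not to implement iRECIST". Protocol 22.3 says a clinically unstable patient "is not required to have repeat tumor imaging for confirmation of PD by iRECIST", and Table 6 requires no more imaging once the investigator has confirmed progression.

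**Rules pointing the other way.** Appendix 1: "Confirmatory scans are required approximately 4 weeks after any scan that indicates either an objective response, stable disease or disease progression". The synopsis (Statistical Methods), the best-overall-response section of Appendix 5 and SAP 15 also require confirmation of progression at least 4 weeks later. Protocol 22.1.3 adds: "For participants who discontinue study treatment without documented disease progression, every effort should be made to continue monitoring disease status by tumor imaging", without naming whose documentation counts.

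**Who reads.** Protocol 22.2 makes BICR by RECIST 1.1 the primary measure for the date of progression. Protocol 22.3 has the investigator take treatment decisions by iRECIST and sends images for possible retrospective BICR. The text that continues imaging until BICR verifies progression is bracketed template wording for studies with PFS as the primary endpoint.

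**Analysis.** SAP 15.2 censors a patient without progression or death at her last evaluable scan, for PFS (Table 3) and for DOR. A death before two consecutive missed assessments (126 days) is a PFS event; progression or death after new anti-cancer therapy is not. SAP 15.2 also states "BICR-assessed PFS and investigator-assessed PFS by RECIST v1.1 will be displayed for Part A" and for Parts B and C. On agreement between readers, SAP 15 plans only this: "Concordance between BICR and Investigator assessments will be summarized at a patient level for BOR".

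**The concern.** BICR is the lead reader for the date of progression, but the end of scanning can be set by the other reader. When the two disagree and scanning stops, a later BICR progression cannot be seen. Kaplan-Meier then treats a woman whose physician has just judged her to be progressing as if her later risk equalled that of patients still stable. Her risk is probably higher, so the censoring is probably informative and the BICR curve is expected to lie too high.

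What is at stake is the 6-month PFS rate, median PFS and DOR by BICR, and the BICR curves. The SAP has no PFS or DOR sensitivity analysis for this, and no table showing how many BICR-censored patients had investigator progression.

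**Working it through.** **The plan's own figure.** Two missed assessments: 2 × 9 weeks × 7 days = 126 days, as SAP 15.2 states. The documents give no expected median PFS, event count or discordance rate, so the size of the effect can only be shown under assumptions.

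**Simple model, 26 weeks.** From the documents: a scan every 9 weeks, so two scans (weeks 9 and 18) by week 26; planned n = 60. Assumed: exponential time to progression with median m = 13, 17.4 or 26 weeks; a share d = 10-30% of investigator progressions that BICR would read one scan later.

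Let S = 2^(−9/m) and p = 1 − S.

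- Reference BICR PFS, with scanning continued: R = (1 − d)S² + dS.
- Kaplan-Meier with discordant patients censored at the investigator's scan: K = [1 − (1 − d)p]².

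For m = 17.4 and d = 20%: S = 0.699, p = 0.301, S² = 0.488.

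- R = 0.8 × 0.488 + 0.2 × 0.699 = 0.530
- K = (1 − 0.241)² = 0.576
- Excess 4.6 points

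**Adding confirmatory scans.** Assume 70% of discordant patients are rescanned 6 weeks later and BICR reads progression there; both curves date progression at that scan, so only the other 30% are lost.

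- Reference: R' = (1 − 0.3d)S² + 0.3dS = 0.94 × 0.488 + 0.06 × 0.699 = 0.501
- Observed: K' = {[1 − (1 − d)p] × S/(S + 0.7dp)}² = (0.759 × 0.699/0.741)² = 0.512
- Excess 1.1 points

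The same formulas over the three medians give, in points of 26-week PFS:

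| d | No confirmatory scan | 70% with confirmatory scan |
|---|---|---|
| 10% | 1.7 to 2.5 | 0.5 to 0.7 |
| 20% | 3.5 to 5.3 | 0.9 to 1.2 |
| 30% | 5.4 to 8.4 | 1.4 to 1.7 |

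If 30% of discordant patients die within the 126-day window and count as events (assumption), the smallest figure without confirmatory scans falls from 1.7 to about 1. For scale, the standard error of a 53% rate at n = 60 is √(0.53 × 0.47/60) = 0.064, or 6.4 points.

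**Second model.** Here each reader has an independent log-normal error around a latent progression time. Assumed: median 3, 5 or 10 months; reader SD 0.1, 0.3 or 0.5; median survival after progression 6 months; 0, 60% or 100% starting new therapy. Discordance came out at about 10-35% of patients. The BICR PFS rate was too high in all 36 scenarios. At week 27 the excess was 1.2-5.8 points without confirmatory scans, and 0.6-2.8 points with such scans in 70% and new therapy in 60%. Median PFS did not move in the 3- and 5-month scenarios, because it is tied to the 9-week grid; it rose by about 1-3 months in the 10-month scenarios. With no new therapy, roughly 20-37% of discordant patients became events through death within 126 days.

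DOR was not simulated.

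**The case against.** The strongest case on the other side is as follows.

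- **Imaging often continues.** Clinically stable patients kept on treatment are rescanned at 4-8 weeks, and the confirmatory-scan rule carries no stability condition. Borderline scans, where readers are most likely to differ, may often belong to such patients. This stands in part. A reader might infer that required imaging simply ends at the investigator's call; the documents conflict on this and do not settle it. Protocol 22.2, which ties treatment discontinuation to BICR, also sits uneasily with 22.3, which leaves treatment decisions to the investigator.
- **Not every such patient is censored.** Death within the window without new therapy is a PFS event. This stands.
- **Investigator PFS and DOR are already planned**, and SAP 7.5 adds investigator PFS curves by PD-L1, HPV type and histology. A gap between readers would therefore be visible. But nothing planned shows whether the gap comes from censoring or from reading differences.
- **Counting investigator progression as an event overcorrects.** In the simple model it gives S² = 0.488 against a reference of 0.530, or 4.2 points too low, where the plan is 4.6 points too high. This stands: it is a bound, not a correction.
- **Little depends on it.** PFS and DOR are secondary and untested, and the only external benchmark in the documents is for ORR. This stands.

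**Conclusion.** The gap is real and modest. Where the investigator calls progression, treatment stops and BICR does not read progression, the plan may leave the patient without further scans and usually censors her in BICR PFS and DOR. Upward bias in the BICR PFS rate is the expected direction. It rests on discordant patients having a higher later risk of BICR progression, which is plausible but not shown in the documents.

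Under assumed discordance of 10-30%, the 26-week excess is about 0.5-2 points if most patients have a confirmatory scan (up to about 3 at week 27 in the second model), and about 1-8 points if none do. Even the larger values are of the order of one standard error. The effect on DOR is the same in kind and unquantified.

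A reader might go further and conclude that the reported BICR PFS and DOR will be too favourable against outside data. The documents do not support that: they give no discordance rate and name no outside PFS or DOR comparator. The primary ORR24 test is unaffected by this mechanism.

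**What to change.** 1. In SAP 15.2, pre-specify a sensitivity analysis of BICR PFS and DOR in which investigator RECIST 1.1 progression without BICR progression is an event at that scan date. Keep the BICR date wherever BICR reads progression. Label the result a conservative lower bound.
2. Report the number of patients censored in each BICR analysis after investigator progression.
3. Extend the concordance table in SAP 15 from BOR to progression status and progression date.
4. Reconcile the imaging rules after progression: Protocol synopsis (Statistical Methods), 22.1.2, 22.1.3, 22.3 with Table 6, Appendix 1, Appendix 5 and SAP 15.

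Items 1 to 3 use data already collected and need no new scans. They should be fixed before database lock. The cost is a few extra tables and a less favourable sensitivity estimate, which may lie below the true BICR rate. The count in item 2 replaces the assumed discordance with the observed one.
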